7.2.3 Safety Analysis

7.2.3.1 Adverse Events (AEs)

The incidence of reported AEs (local/systemic/other) after investigational product administration shall be calculated by cohort, with the relevant 95% confidence intervals and number of events being estimated.

The AEs shall be categorized according to severity, causal relationship with the investigational products, and the number of occurrences and percentage shall be calculated. The numbers of AEs, ADRs, and SAEs as well as the numbers of subjects experiencing them shall be calculated to estimate incidence.

Additional analysis shall be conducted for AESIs using identical methods applied to AEs.

All AEs shall be analyzed according to system organ class (SOC) and preferred term (PT) using the latest version of the MedDRA.

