8.7 Other Statistical Considerations

The analysis will be carried out according to considerations as follows. If additional considerations on each analysis item is required, the corresponding options will be described in '10.1 Derivation'.

- In Cohort 1, Cohort 2, Cohort 3, 'Baseline' is '1st Hospitalization (Before 1st injection)' visit. And in Cohort 4 and Cohort 5, 'Baseline' is 'Before 1st injection' visit.
- The criteria for converting day to month are as follows: 1month=30days
- When calculating percentage for categorical variables except for 'Analysis Sets' summary, the denominator is the number of subjects in each cohort. Only in case of analysis by type of Medical History/Surgical History/Prior Medication/Concomitant Medication, the denominator is the number of subjects having Medical History/Surgical History/Prior Medication/Concomitant Medication in each cohort.
- The calculating criteria of percentage for 'Analysis Sets' summary will be described in 9.1 Disposition of Subjects'.
- The 95% confidence interval will be estimated by using exact method.

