9.5 Safety Evaluation

9.5.1 Adverse Events

The summary table for the following AE will be presented by each cohort. In the summary table, the number and proportion of subjects to whom following AE occurred, and its 95% confidence interval and the number of following AEs will be estimated.

- Adverse Event
- Adverse Drug Reaction^a
- Serious Adverse Event
- Serious Adverse Drug Reaction^a
- Early Withdrawal due to AE^b
- Adverse Event of Special Interest^c

^a Adverse Drug Reaction: AE including whose 'Causal Relationship with IP' is assessed "Definitely related", "Probably related", "Possibly related", "Unknown"

^b Early Withdrawal due to AE: AE whose 'Reason for discontinuation' of 'Study Conclusion' is

'Occurrence of an AE that leads treatment discontinuation' and 'Action taken to IP' is "Interrupted"
 c Adverse Event of Special Interest: It is Thrombosis/embolism, Spontaneous bleeding, Inhibitor generation/seroconversion, Anaphylaxis and collected in other AE only

Additionally, the summary table for the following local¹/systemic²/other³ AE will be presented by each cohort. In the summary table, the number and proportion of subjects to whom local/systemic/other AE occurred, and its 95% confidence interval and the number of following AEs will be estimated.

- Adverse Event
- Adverse Drug Reaction
- Serious Adverse Event
- Serious Adverse Drug Reaction
- Early Withdrawal due to AE

¹ Local AE: AEs occurring within 1 hour after the administration of investigational products including pain, tenderness, erythema/redness, urticaria/pruritus, and induration/swelling

² Systemic Adverse Event: AEs occurring within 1 hour after the administration of investigational products including fever, fatigue/malaise, chill/pyrexia, , headache, myalgia, arthritis(arthralgia), decreased appetite/loss of appetite, diarrhea, vomiting, constipation, abdominal pain, mucosal skin reaction/rash, vasovagal syncope, dizziness, cough, acute bronchospasm, dyspnea, and hypersensitivity

³ Other Adverse Event: AEs other than local or systemic AEs occurring after the administration of investigational products

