For following item, the number and proportion of subjects with following local AE and systemic AE according to reported term, other AE according to the SOC, PT and its 95% confidence interval and the number of following local AE and systemic AE according to reported term, other AE according to the SOC, PT will be estimated. If one subject has 2 or more AE in one category, it will be analyzed as one in the category. Also, the same subject may appear in different category in duplicate.

- Adverse Event
- Adverse Drug Reaction
- Serious Adverse Event
- Serious Adverse Drug Reaction
- Adverse Event of Special Interest

For AE, local/systemic/other AE, AESI, the number of AEs and its percentage (%) by each cohort

according to following AE item will be presented.

- Seriousness
- Severity
- Outcome
- Action Taken to IP
- Causal Relationship with IP
- Causal Relationship with others
- Treatment Given for AE

The following AEs will be listed.

- Local Adverse Drug Reaction
- Systemic Adverse Drug Reaction
- Other Adverse Drug Reaction
- Local Serious Adverse Event
- Systemic Serious Adverse Event
- Other Serious Adverse Event
- Adverse Event of Special Interest
- Adverse Event of subjects whose Early Withdrawal due to Adverse Event
- Other Adverse Event whose reported term is 'Nab positive' or 'ADA positive'
- Other Adverse Event whose PT term include 'injection site'
- Adverse Event (each patient)

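### The SAP's only applicable denominator rule divides AE counts by subjects in the severity, causality and outcome tables, so those percentages can exceed 100%, and no table shows subjects by worst severity

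*Combined protocol and SAP*

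**What the plan says.** **The general rule.** SAP 8.7 says that, for categorical percentages, "the denominator is the number of subjects in each cohort". Besides the Analysis Sets summary, the only other exception is the by-type breakdown of medical and surgical history and of prior and concomitant medication. AEs are in neither exception. SAP 8.7 refers any further considerations to SAP 10.1, which contains no AE rule.

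**The AE-characteristic tables.** For all AEs, for local, systemic and other AEs, and for AEs of special interest (AESIs), SAP 9.5.1 asks for "the number of AEs and its percentage (%) by each cohort". The items are seriousness, severity, outcome, action taken, causal relationship with the product, causal relationship with other factors, and treatment given. SAP 10.2 lists all seven with their categories, so the rule in 8.7 applies to them.

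**The incidence tables.** Elsewhere SAP 9.5.1 is explicit that subjects are counted: "the number and proportion of subjects to whom following AE occurred, and its 95% confidence interval and the number of following AEs will be estimated". For the tables by reported term or by SOC and PT it adds: "If one subject has 2 or more AE in one category, it will be analyzed as one in the category". That sentence comes before the AE-characteristic tables and is not repeated for them.

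**The protocol.** Section 7.2.3.1 says of severity and causality that "the number of occurrences and percentage shall be calculated", without a denominator.

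**The concern.** The numerator in the AE-characteristic tables is events, and the only denominator the SAP supplies for them is subjects. One subject can contribute several events, so the quotient is a mean count multiplied by 100. It is neither a share of events nor a proportion of subjects.

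This is a phase 1 study with a safety objective, 3 to 5 subjects per cohort and up to 10 administrations per subject, so the problem could appear at quite ordinary event counts. A reader who takes the mild or severe percentage as the severity mix would be misled, and more so in the repeat-dose cohorts. A second gap lies beside it: the subject-level tables cover AEs, adverse drug reactions (ADRs), serious AEs (SAEs), serious ADRs, withdrawals and AESIs, but none counts subjects by their worst severity.

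**Working it through.** The documents print no AE percentage, so there is no planned figure to reproduce. The check is direct arithmetic.

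**Inputs from the documents**
- Cohorts 1, 2 and 3: n = 3 each, 2 administrations per subject (SAP 2).
- Cohort 4: n = 5, 6 administrations per subject (SAP 2).
- Cohort 5: n = 3 to 5 (SAP 2), 1 IV + 9 SC = 10 administrations per subject (Protocol 5.2.4).

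**Assumptions, not in the documents:** 0.1 to 1.0 AE per administration, with 80% of AEs mild in every cohort.

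**Formulas**
- Literal reading of 8.7 with 9.5.1: 100 × (AEs in category) / (subjects in cohort).
- Share-of-events reading: 100 × (AEs in category) / (all AEs in cohort).

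**Step 1: when a category passes 100%.** Under the literal reading this happens once the category holds n + 1 AEs:
- n = 3: 100 × 4/3 = 133.33%
- n = 5: 100 × 6/5 = 120%

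**Step 2: whether categories sum to 100%.** Take 8 mild and 2 moderate AEs.
- Literal, n = 3: 100 × 8/3 = 266.67% and 100 × 2/3 = 66.67%, sum 333.33%.
- Literal, n = 5: 160% and 40%, sum 200%.
- Share of events, either n: 80% and 20%, sum 100%.

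**Step 3: what the figure tracks.** With full planned dosing, AEs per subject = rate × administrations, so the literal mild percentage is 100 × 0.8 × rate × administrations, and n cancels.

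| AEs per administration | Cohorts 1–3 (2) | Cohort 4 (6) | Cohort 5 (10) | Share of events, all cohorts |
|---|---|---|---|---|
| 0.1 | 16% | 48% | 80% | 80% |
| 0.25 | 40% | 120% | 200% | 80% |
| 0.5 | 80% | 240% | 400% | 80% |
| 1.0 | 160% | 480% | 800% | 80% |

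The severity mix is the same in every cell. Only the number of events per subject changes.

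**Step 4: why a subject-level row is also needed.** Suppose three severe AEs are the only events in a 3-subject cohort. The literal reading prints 3/3 = 100% and the share-of-events reading also prints 3/3 = 100%, whether the events fell in one subject or in three. A worst-severity row separates the two cases: 1/3 = 33.33% against 3/3 = 100%.

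**The case against.** The strongest reply is that SAP 9.5.1 already means a share of AEs. The percentage follows directly on the number of AEs, and where the SAP wants subjects it says so. A specific instruction can override a general one. The mock tables, which are not in the text available here, may show the intended denominator, and SAP 10.1 allows formulas to be added there. This reading is reasonable, so miscalculation is not certain. But it departs from the only denominator rule the SAP states for these items, and the SAP does not say that it does.

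One could also extend the one-per-subject rule to these tables, which would make the subject denominator correct. The text attaches that rule to the preceding tables, and the numerator here is stated as AEs.

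The effect is also limited, and this stands. The main AE summaries give subjects, exact 95% intervals and separate event counts. ADR and SAE incidence already provide subject-level views of causality and seriousness. Per-patient listings let a reader trace each event in cohorts this small.

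Three stronger conclusions might be inferred, and the documents do not support them:
- **That every categorical percentage is affected.** SAP 8.7 names two exceptions, and subject-based tables match its rule.
- **That results cannot be compared across cohorts.** The literal figure is comparable as a mean AE count per subject. What it does not convey is the distribution of severity, causality or outcome. Counts rising with 2, 6 or 10 administrations is a matter of exposure and would occur under any denominator.
- **That the by-type history and medication denominator is an error.** It is stated openly and gives a legitimate conditional percentage. The separate Yes/No items keep the cohort denominator.

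**Conclusion.** The point holds as a mismatch between a stated rule and the tables it governs. Applied as written, SAP 8.7 and 9.5.1 yield 100 × mean AEs per subject in each category. That figure exceeds 100% from 4 AEs in a 3-subject cohort or 6 in a 5-subject cohort, need not sum to 100% across categories, and follows event frequency rather than the severity or causality mix. These thresholds need no assumption beyond the literal reading. The table in the working also rests on assumed AE rates and an assumed 80% mild share, and only illustrates the pattern.

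The consequence is confined to descriptive AE-characteristic tables. Subject-level incidence of AEs, ADRs, SAEs and AESIs, with exact intervals, is untouched. The missing worst-severity tabulation is a real gap under either reading. The SAP should be corrected, but the point does not undermine the safety analysis as a whole.

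**What to change.** In SAP 8.7, add a third exception, repeated in 9.5.1: in tables of AE characteristics, the denominator is the total number of AEs in the cohort within the AE class shown (all, local, systemic, other, AESI). In SAP 9.5.1, add rows counting each subject once at worst severity, with subjects in the cohort as denominator. Check that the mock tables carry the same denominators in their headers or footnotes.

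AEs per administration could be shown as an optional extra, but it is not part of the correction.

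The cost is a few sentences of SAP text and an edit to the table shells. Severity is already recorded for each AE, so no new data are needed.

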8.8 Reporting Conventions

- The descriptive statistics (mean, standard deviation, 25th percentile, median, 75th percentile, minimum, maximum, percentage) rounds to 2 decimal places.
- If the calculated percentage is less than 0.01, it will be presented as '<0.01'.

9. Evaluation of Study Data

All analysis will be applied for Safety Analysis Set as follows.

Analyses	Safety Analysis Set
Demographics	✓
Medical History	✓
Prior and Concomitant Medications	✓
Safety Evaluation	✓

9.1 Disposition of Subjects

The following 'Patient disposition' and 'Analysis Sets' will be presented as a figure.

Patient disposition

- The number of screening subjects
- The number of screening failure subjects and reason for screening Failure
- The number of enrolled subjects
- The number of early withdrawal subjects and reasons for early withdrawal
- The number of study completion subjects

Analysis Sets

- The number of enrolled subjects
- The number of Safety Analysis Set of enrolled subjects
- The number of subjects excluded from Safety Analysis Set of enrolled subjects and the criterion of excluded from Safety Analysis Set

Additionally for 'Analysis Sets', the table including the frequency and percentage will be presented.

The following subjects will be listed.

- Listing of Subjects with early withdrawal
- Listing of Subjects enrolled in multiple cohorts

9.2 Demographics

For following continuous variable, the descriptive statistics for each cohort will be presented.

- Age
- Height
- Weight

For following categorical variables, the descriptive statistics for each cohort will be presented.

- Gender
- Age

The above demographics for each subjects will be listed.

9.3 Medical History

For following continuous variable, the descriptive statistics for each cohort will be presented.

- Duration of Hemophilia B

For following categorical variables, the descriptive statistics for each cohort will be presented.

- Duration of Hemophilia B
- Family History of Hemophilia B
- History of FIX Inhibitor
- Family History of FIX Inhibitor
- FIX activity \leq 2% before screening visit
- FIX product 150 exposure days at the time of screening
- Medical History^a
- Surgical History^b

^a Medical History: Any past or concomitant disease at screening (last 3months)

^b Surgical History: Any surgical history from prior 3 months ago to screening visit

The medical history and surgical history will be classified as SOC under the classification standard of recent version MedDRA. If one subject has 2 or more medical history/surgical history in one category (SOC), it will be analyzed as one in the category. Also, the same subject may appear in

different category in duplicate.

9.4 Prior and Concomitant Medications

For following categorical variables, the descriptive statistics for each cohort will be presented.

- Prior Medication^a
- Concomitant Medication^b

^a Prior Medication: any drugs started from 3 months before screening visit to 1st injection

^b Concomitant Medication: any drugs started after 1st injection

The prior and concomitant medication will be classified as Level 1, Level 2 under the classification standard of recent version WHODDE. If one subject taken 2 or more medication in one category (Level 1, Level 2), it will be analyzed as one in the category. Also, the same subject may appear in different category in duplicate.

9.5 Safety Evaluation

9.5.1 Adverse Events

The summary table for the following AE will be presented by each cohort. In the summary table, the number and proportion of subjects to whom following AE occurred, and its 95% confidence interval and the number of following AEs will be estimated.

- Adverse Event
- Adverse Drug Reaction^a
- Serious Adverse Event
- Serious Adverse Drug Reaction^a
- Early Withdrawal due to AE^b
- Adverse Event of Special Interest^c

^a Adverse Drug Reaction: AE including whose 'Causal Relationship with IP' is assessed "Definitely related", "Probably related", "Possibly related", "Unknown"

^b Early Withdrawal due to AE: AE whose 'Reason for discontinuation' of 'Study Conclusion' is

'Occurrence of an AE that leads treatment discontinuation' and 'Action taken to IP' is "Interrupted"
 c Adverse Event of Special Interest: It is Thrombosis/embolism, Spontaneous bleeding, Inhibitor generation/seroconversion, Anaphylaxis and collected in other AE only

Additionally, the summary table for the following local¹/systemic²/other³ AE will be presented by each cohort. In the summary table, the number and proportion of subjects to whom local/systemic/other AE occurred, and its 95% confidence interval and the number of following AEs will be estimated.

- Adverse Event
- Adverse Drug Reaction
- Serious Adverse Event
- Serious Adverse Drug Reaction
- Early Withdrawal due to AE

¹ Local AE: AEs occurring within 1 hour after the administration of investigational products including pain, tenderness, erythema/redness, urticaria/pruritus, and induration/swelling

² Systemic Adverse Event: AEs occurring within 1 hour after the administration of investigational products including fever, fatigue/malaise, chill/pyrexia, , headache, myalgia, arthritis(arthralgia), decreased appetite/loss of appetite, diarrhea, vomiting, constipation, abdominal pain, mucosal skin reaction/rash, vasovagal syncope, dizziness, cough, acute bronchospasm, dyspnea, and hypersensitivity

³ Other Adverse Event: AEs other than local or systemic AEs occurring after the administration of investigational products

For following item, the number and proportion of subjects with following local AE and systemic AE according to reported term, other AE according to the SOC, PT and its 95% confidence interval and the number of following local AE and systemic AE according to reported term, other AE according to the SOC, PT will be estimated. If one subject has 2 or more AE in one category, it will be analyzed as one in the category. Also, the same subject may appear in different category in duplicate.

- Adverse Event
- Adverse Drug Reaction
- Serious Adverse Event
- Serious Adverse Drug Reaction
- Adverse Event of Special Interest

For AE, local/systemic/other AE, AESI, the number of AEs and its percentage (%) by each cohort

according to following AE item will be presented.

- Seriousness
- Severity
- Outcome
- Action Taken to IP
- Causal Relationship with IP
- Causal Relationship with others
- Treatment Given for AE

The following AEs will be listed.

- Local Adverse Drug Reaction
- Systemic Adverse Drug Reaction
- Other Adverse Drug Reaction
- Local Serious Adverse Event
- Systemic Serious Adverse Event
- Other Serious Adverse Event
- Adverse Event of Special Interest
- Adverse Event of subjects whose Early Withdrawal due to Adverse Event
- Other Adverse Event whose reported term is 'Nab positive' or 'ADA positive'
- Other Adverse Event whose PT term include 'injection site'
- Adverse Event (each patient)

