10.1 Derivation	21
10.2 Categorization	22
Appendix.....	25

Abbreviations

Abbreviations	Definition
ADR	Adverse Drug Reaction
AE	Adverse Event
AESI	Adverse Event of Special Interest
CS	Clinical Significance
FIX	Factor IX
HIV	Human Immunodeficiency Virus
IP	Investigational Products
IU	International Unit
MedDRA	Medical Dictionary for Regulatory Activities
NCS	Non Clinical Significance
PT	Preferred Term
SAP	Statistical Analysis Plan
SAS	Statistical Analysis System
SOC	System Organ Class
TLFs	Tables, Listings, Figures
WHODDE	World Health Organization Drug Dictionary Enhanced

1. Purpose of the Statistical Analysis Plan

The purpose of this document is documentation for the details for analyzing the data collected in the ISU304-001 study.

This document is based on the statistical analysis method described in protocol, and results of the analysis in this document will be included in the clinical study report.

If any additional analysis undescribed in this document is required, it will be written in separate document (ex. Additional Analysis Plan).

2. Study Features

Study title	A Phase 1, Open-label, Multi-center, Dose-escalation Study to Investigate the Safety, Pharmacokinetics and Pharmacodynamics of ISU304 in Previously Treated Hemophilia B Patients
Study duration	Approximately 24 months after the protocol approval from the institutional review boards (IRBs)
Indication	Previously treated hemophilia B patients
Study objective	To investigate the safety, pharmacokinetics and pharmacodynamics of ISU304 (recombinant factor IX with increased activity) in previously treated hemophilia B patients
Phase and design	Phase 1, open-label, multi-center, dose-escalation
Investigational products	
 • Study drug: ISU304 75, 150IU/kg, intravenous or subcutaneous administration • Active control: BeneFIX 75 IU/kg, intravenous administration • Rescue drug: Treatment currently used by subject to treat hemophilia B

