4.2 Final Analysis

The statistical analysis of this study will be performed after all data is collected and database lock is completed.

5. Changes to the Planned Analyses in the Protocol

The PK/PD analysis is described in Protocol but PK/PD analysis will be conducted at the designated central laboratory (HTI). So this document does not include this analysis.

6. Analysis Sets

Safety Analysis Set

All subjects who receive at least one dose of investigational products

7. Protocol Deviations

The additional protocol deviations other than analysis set criteria described in '6. Analysis Sets' are not considered.

8. General Specifications for Statistical Analyses

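### AE incidence is tabulated by cohort only, so the Cohort 1 row combines BeneFIX with ISU304 and the Cohort 2 and 3 rows combine ISU304 IV with SC

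*Combined protocol and SAP*

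**What the plan says.** On the tabulation unit, the two documents agree. Protocol 7.2.3.1: "The incidence of reported AEs (local/systemic/other) after investigational product administration shall be calculated by cohort". SAP 9.5.1: "The summary table for the following AE will be presented by each cohort". The SAP applies this to AEs, ADRs, SAEs, serious ADRs, AE withdrawals and AESIs, and again to the local/systemic/other breakdown. SAP 8.7 makes the number of subjects in the cohort the denominator and calls for exact 95% intervals.

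SAP 9.5.1 defines an ADR by its relationship to the investigational product. SAP section 2 counts the comparator among those products: "Active control: BeneFIX 75 IU/kg, intravenous administration".

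On the content of the cohorts, protocol 4.4 gives:
- Cohort 1 (n=3): BeneFIX 75 IU/kg IV, then ISU304 75 IU/kg IV.
- Cohort 2 (n=3): ISU304 75 IU/kg IV, then 75 IU/kg SC.
- Cohort 3 (n=3): ISU304 75 IU/kg IV, then 150 IU/kg SC.
- Cohort 4 (n=5): daily ISU304 150 IU/kg SC.
- Cohort 5 (n=3 to 5): ISU304 IV, with daily SC dosing that starts about 30 minutes later (protocol 5.2.4).

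On coding, protocol 7.2.3.1 says "All AEs shall be analyzed according to system organ class (SOC) and preferred term (PT) using the latest version of the MedDRA". SAP 9.5.1 tabulates "local AE and systemic AE according to reported term, other AE according to the SOC, PT". SAP section 5 declares only the PK/PD analysis as a change from the protocol.

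**The concern.** The objective in protocol 1.3 is the safety of ISU304. AE collection starts at the first investigational product (protocol 8.2), which in Cohort 1 is BeneFIX. A reaction to BeneFIX therefore enters the same AE and ADR incidence as a reaction to ISU304. The type of event does not help to separate them, because protocol 2.1.3 expects the two products to have similar adverse events.

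In Cohorts 2 and 3 the product is the same but the route differs. Tolerability of SC injection is a named assessment (protocol 5.1.6), yet the row for each cohort pools IV and SC events.

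The same structure affects laboratory tests, vital signs and ECG. SAP 8.7 fixes baseline before the first injection. SAP 9.5.2, 9.5.4 and 9.5.5 present change from there to end of cohort, so in Cohorts 1 to 3 that change spans both treatments.

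**Working it through.** The documents state no AE rate, so there is no planned figure to reproduce. The check is what a cohort row can and cannot show.

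**Inputs.** n=3 in each of Cohorts 1 to 3 (protocol 4.4); the denominator is cohort subjects and intervals are exact 95% (SAP 8.7).

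**Formula.** For x patients of n, the exact (Clopper-Pearson) limits are the 2.5% quantile of Beta(x, n−x+1) and the 97.5% quantile of Beta(x+1, n−x).
- 0/3: 0 to 1 − 0.025^(1/3) = 0% to 70.8%
- 1/3: 1 − 0.975^(1/3) = 0.8%, to 90.6%
- 2/3: 9.4% to 99.2%

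**Cohort 1.** Suppose one patient has an AE after BeneFIX only. The row reads 1/3 (0.8% to 90.6%). ISU304's figure is 0/3 (0% to 70.8%). If instead the single AE follows ISU304, the row still reads 1/3. The table is the same in the two cases.

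**Cohort 2 or 3.** Suppose one patient has an AE after IV only and another after SC only. The row reads 2/3 (9.4% to 99.2%). Each route's figure is 1/3 (0.8% to 90.6%).

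**How much of the trial is affected.** Planned cohort places are 3+3+3+5+3 = 17 to 3+3+3+5+5 = 19. Cohort 1 is 3/19 to 3/17, or 16% to 18%. Cohorts 2 and 3 are 6/19 to 6/17, or 32% to 35%. These are places, not distinct patients, because protocol 3.3 counts repeat participants.

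**Whether a split is possible with the data collected.**
- Dose date, time and route are in the CRF (protocol 5.1.11).
- AE onset date is recorded (protocol 5.1.15 and 8.2).
- Doses 1 and 2 are at least 4 days apart (protocol 5.2.1.5 and 5.2.2.5).
- Local and systemic AEs are defined as falling within 1 hour of a dose (protocol 5.1.15), so the date alone ties them to a period.
- Onset time is recorded only for AESIs (protocol 5.1.15). Other AEs dated on the day of dose 2 are therefore ambiguous and need a rule.
- Laboratory tests and ECG at the second hospitalisation, and vital signs just before dose 2, are scheduled (protocol 5.2.1.5 and 5.2.2.5).

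**The case against.** By-cohort tabulation is the protocol's own rule, and the SAP follows it. The cohort is also the unit of escalation and of DSMB review (protocol 4.1 and 9.9). With three patients and descriptive aims, listings carry most of the information, and SAP 9.5.1 plans one of all AEs for each patient, besides ADR, SAE and AESI listings. No stated test or decision uses a treatment-level AE rate. The mock tables are an appendix whose content is not shown, so a by-period layout there cannot be ruled out. All of this stands. It limits the weight of the point but does not remove it, since a listing is not a prespecified incidence table and the SAP text describes no period split.

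Several stronger readings are tempting but not supported:
- That SAP 8.3 bars the split by planning no subgroups. That section is naturally read as concerning subsets of patients; product, route and period vary within the same patient.
- That inhibitor findings are blurred between products. Antibodies to BeneFIX and to ISU304 are tested separately (protocol 5.1.10), and all results are listed (SAP 9.5.6).
- That most of Cohort 1's AE time precedes ISU304. The share depends on which window applies: protocol 8.2 stops at end of cohort, 8.4.2 tracks to 14 days after the last dose, and 5.2.6 checks AEs at the post-study visit. Calendar time is in any case a poor guide for events confined to 1 hour after a dose.
- That the documents support a probability of miscounting. They give no per-period AE risk, so any such figure would be assumed.
- That a table combining early and late injection-site reactions is owed. No document requires one.

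**Conclusion.** The point holds in a limited form. As the text stands, the Cohort 1 incidence belongs to BeneFIX and ISU304 jointly, and the Cohort 2 and 3 incidences belong to IV and SC jointly. The size is one patient in three: a single BeneFIX-only AE moves the tabulated figure from 0/3 to 1/3. Cohort 4 is unaffected. Cohort 5 cannot be cleanly split, because the IV and first SC doses are about 30 minutes apart.

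Splitting does not narrow the intervals, since each line keeps n=3; the gain is correct attribution. A reader might wish to pool all ISU304 75 IU/kg IV periods from Cohorts 1 to 3, which would give 3+3+3 = 9 subject-periods. Patients may enrol in more than one cohort (protocol 3.3; SAP 9.1 lists them), so that pool could count one person twice as if independent.

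The only SAP departure from the protocol here is the use of reported terms for local and systemic AEs. It is real, undeclared and minor: these events have named term lists and their own assessment tables, and protocol 8.2 already requires MedDRA terms at recording.

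The conclusion assumes that the unseen mock tables add no period split.

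**What to change.** - Keep the cohort tables. For Cohorts 1 to 3, add the same AE/ADR/SAE/AESI and local/systemic/other tables by administration period within cohort, defined by the most recent product, dose and route at onset, with n=3 per line. Leave Cohorts 4 and 5 as their own groups, and do not pool across cohorts in a way that treats a repeat participant as independent.
- State a rule for events dated on the day of dose 2.
- Show which Cohort 1 period-2 events the investigator attributes to the earlier BeneFIX dose. SAP 10.2 has a single causality item for the investigational product, so this may need a query if the CRF does not name the product.
- For period 2 of Cohorts 1 to 3, add change in laboratory tests, ECG and vital signs from the last value before dose 2.
- Tabulate local and systemic AEs by SOC and PT, or declare the reported-term choice in SAP section 5.

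The cost is SAP text and a little programming; apart from that possible query, no new data are needed. The drawback is that late events after dose 2 go to the latest dose by convention. This could credit a delayed BeneFIX reaction to ISU304, which is why the attribution display is needed alongside.
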